#### **8.1.2.2. Adverse Event Severity**

The term “severe” is used to describe the intensity of an AE; the event itself could be of relatively minor clinical significance (e.g., ‘severe’ headache). This is not the same as a “serious” AE.

The severity of the AE will be graded by the Investigator according to the NCI CTCAE Grading Scale, v. 5.0 (the NCI CTCAE files can be accessed online at the following URL: <http://evs.nci.nih.gov/ftp1/CTCAE/About.html>).

If there is not a specific NCI CTCAE grading scale for an AE, the severity will be characterized as mild, moderate, severe, or life-threatening, according to the following definitions:

- Grade 1 (mild) events are usually transient in nature and do not interfere with the patient’s daily activities.
- Grade 2 (moderate) events introduce a low level of inconvenience or concern to the patient and may interfere with daily activities.
- Grade 3 (severe) events interrupt the patient’s usual daily activities.
- Grade 4 events are those that are considered to be life-threatening.

#### **8.1.3. Adverse Event Causality**

The Investigator will make a judgment regarding the relationship of the AE to study treatment, as defined below.

- Not related: These events will lack a strong temporal relationship of the event to the study treatment, making a causal relationship not reasonably possible. Exposure to other drugs, therapeutic interventions, or underlying conditions may provide a sufficient explanation for the event.
- Related: There is a temporal relationship of the event to the study treatment making a definitive relationship, and the event is more likely explained by exposure to the study treatment than by any other drugs, therapeutic interventions, or underlying conditions.

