## 5.7. Dose Modifications

Each dose modification or treatment delay must be documented, including the respective reason. The reason for dose modification should be directly related to a selinexor-associated AE, and not due to disease symptom/sign or to other medications.

For all Grade  $\geq 3$  hematological or non-hematological AEs that are NOT selinexor related, after consultation with the Medical Monitor and at the discretion of the Investigator, selinexor dosing may be maintained.

Selinexor should be discontinued for all selinexor-related life-threatening (Grade 4) AEs.

[Table 4](#) summarizes the selinexor dose levels; [Table 5](#) describes supportive care and dose adjustment guidelines. Deviations from the guidelines are permitted after discussion between the Sponsor and the treating physician.

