- *Suspected adverse reaction*: Any adverse event for which there is a reasonable possibility that the drug caused the adverse event. For the purposes of IND safety reporting, "reasonable possibility" means there is evidence to suggest a causal relationship between the drug and the adverse event. Suspected adverse reaction implies a lesser degree of certainty about causality than adverse reaction, which means any adverse event caused by a drug.
- *Unexpected adverse event or unexpected suspected adverse reaction*: An adverse event or suspected adverse reaction is considered "unexpected" if it is not listed in the investigator brochure or is not listed at the specificity or severity that has been observed; or, if an investigator brochure is not required or available, is not consistent

with the risk information described in the general investigational plan or elsewhere in the current application, as amended. For example, under this definition, hepatic necrosis would be unexpected (by virtue of greater severity) if the investigator brochure referred only to elevated hepatic enzymes or hepatitis. Similarly, cerebral thromboembolism and cerebral vasculitis would be unexpected (by virtue of greater specificity) if the investigator brochure listed only cerebral vascular accidents. "Unexpected," as used in this definition, also refers to adverse events or suspected adverse reactions that are mentioned in the investigator brochure as occurring with a class of drugs or as anticipated from the pharmacological properties of the drug, but are not but are not specifically mentioned as occurring with the particular drug under investigation.

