### **8.1.2. Recording of Adverse Events**

All AEs that begin or worsen after the patient has provided informed consent will be recorded. Those AEs that occur prior to study dosing, can be captured in the patient's baseline conditions, however if any of these AEs are considered, serious, these are to be reported both to Pharmacovigilance and documented in the eCRF AE log. For events that are considered by the Investigator to be related to the study drug, the monitoring of the AE should be continued through the end of the study, for at least 30 days following last dose of study drug (if the end of the study is within 30 days of the last dose of study drug), or until the AE has resolved.

Investigators should use medical judgment in determining whether a particular symptom or sign is considered to be a part of COVID-19 infection clinical course or not and report them or not as AEs according to such determination. When a clear determination cannot be made by the investigators, a sign or symptom should be reported as AEs. All deaths irrespective of cause of death including due to COVID-19 during the study should be reported to the Sponsor using an SAE form.

Adverse events (including laboratory abnormalities that constitute AEs) should be described using a diagnosis whenever possible, rather than individual underlying signs and symptoms. When a clear diagnosis cannot be identified, each sign or symptom should be recorded as a separate AE.

The Investigator should ask the patient non-leading questions to determine if any AEs have occurred during the study, since the last study visit. Adverse events may also be recorded when they are volunteered by the patient, or through physical examination, laboratory tests, or other clinical assessments.

An AE should be followed until its resolution or until it is judged to be permanent, and assessment should be made at each visit (or more frequently, if necessary) of any changes in severity of the event, the suspected relationship to the study treatment, the interventions required to treat the event, and the outcome.

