#### **8.2.1.4. Suspected Unexpected Serious Adverse Reactions**

Suspected unexpected serious adverse reactions (SUSARs) are SAEs that are unexpected and judged by the Investigator or Karyopharm to be related to the study treatment administered. All SUSARs will be collected and reported to the competent authorities and relevant ethics committees in accordance with the FDA's "Safety Reporting Requirements for Investigational New Drugs and Bioanalytical/Bioequivalence Studies" or as per national regulatory requirements in participating countries.

If required by local regulations, the Investigator is responsible for notifying his/her IRB or local ethics committee of all SAEs.

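### Protocol Section 8.1.3 has no category for an adverse event that study drug may reasonably have caused but that another cause explains at least as well

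*Protocol*

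**What the plan says.** Section 8.1.3 of the protocol asks the investigator for one of two answers.

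- *Related*: "There is a temporal relationship of the event to the study treatment making a definitive relationship", and also "the event is more likely explained by exposure to the study treatment than by any other drugs, therapeutic interventions, or underlying conditions". The two conditions are joined, so both must be met.
- *Not related*: the event lacks a strong temporal relationship to study treatment, "making a causal relationship not reasonably possible". A further sentence adds: "Exposure to other drugs, therapeutic interventions, or underlying conditions may provide a sufficient explanation for the event".

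Section 8.1.1 defines a suspected adverse reaction by a reasonable possibility of drug causation. For IND safety reporting, it says, that term "means there is evidence to suggest a causal relationship between the drug and the adverse event". It adds that a suspected reaction carries less certainty than an adverse reaction. It asks for no comparison with other causes.

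SAP Section 8.1 keeps the same two categories and supplies no definition of its own. Protocol Section 8.2.1.4 then describes SUSARs as "SAEs that are unexpected and judged by the Investigator or Karyopharm to be related to the study treatment administered", and Section 5.7 states: "Selinexor should be discontinued for all selinexor-related life-threatening (Grade 4) AEs".

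**The concern.** Two standards for one judgement stand a page or two apart, and the stricter one is what the investigator is told to apply. The setting makes the difference matter. Every patient has severe COVID-19, antivirals and anti-inflammatory agents are permitted (Section 4.1), and investigators are blinded (Section 6.4). Competing explanations will be common.

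The protocol's own figures show that the symptoms overlap. Section 1.2 gives fatigue 38%, headache 14% and dyspnea 19% among COVID-19 cases. Table 7 in Appendix 2 gives 60%, 36% and 12% for the same terms in 25 patients on low-dose selinexor. These are different, uncontrolled populations, so the figures show only that overlap exists, not how many events are affected.

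If investigators handle the ambiguous events differently, the related-AE tables become hard to interpret, and rules that turn on relatedness may be applied unevenly from site to site.

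**Working it through.** No arithmetic applies. The check sets the two definitions against every kind of event and then traces where the label is used.

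**Step 1: three kinds of event**

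| Event | Section 8.1.1 | Section 8.1.3 |
|---|---|---|
| (a) Definite temporal link, drug more likely than any other cause | Suspected reaction | Related |
| (b) Drug causation not reasonably possible | Not a suspected reaction | Not related |
| (c) Drug causation reasonably possible, another cause at least as likely | Suspected reaction | Fails *Related*; does not fit *Not related* |

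Rows (a) and (b) agree. Row (c) is the conflict. It fails *Related* because the drug is not the more likely explanation. It fails *Not related* because causation is reasonably possible. Section 8.1.3 is thus also inconsistent within itself: one category uses a more-likely-than-others test and the other a reasonable-possibility test, so they are not complementary.

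The comparison in *Related* can be read as drug against each other cause singly, or against all of them together. The single-cause reading is easier to meet, but row (c) remains under both.

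**Step 2: do the two standards meet in practice?** Section 8.1.1 ties its explanation of reasonable possibility to IND safety reporting. Section 8.2.1.4 rests SUSAR reporting on a judgement of relatedness, so they meet there.

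**Step 3: where the label is used**

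- Related-AE summaries rest on the investigator's determination (Protocol Section 9.4.2); SAP Section 8.1 tabulates treatment-related TEAEs.
- AEs more than 30 days after the last dose count as TEAEs only if the investigator judges them related (SAP Section 8.1).
- A SUSAR needs a related judgement by the investigator or the sponsor (Section 8.2.1.4).
- Removal from treatment for Grade 4 events (Sections 5.7 and 6.2), dose adjustment (Section 5.7 and the footnote to Table 5) and continuation of dosing for a further two weeks (Section 3.1) all refer to relatedness.

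**Step 4: where it is not used**

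- Every SAE up to 30 days after treatment goes to the sponsor within 24 hours whatever its cause (Section 8.2.1.3).
- The DSMB receives all AE reports regardless of the investigator's causality call (Section 10.5).
- The halting criteria compare arms on death, invasive ventilation and nausea or vomiting without attribution (Section 9.5).
- All-causality TEAE tables by arm are planned (SAP Section 8.1).

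A missing causality answer counts as related (Protocol Section 9.1.1, SAP Section 4.4.4). That does not help when an investigator actually records *Not related*.

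**The case against.** The strongest reply is that little depends on this label and that other provisions cover much of what does.

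- **Follow-up.** Section 8.1.2 has a rule for related events ("For events that are considered by the Investigator to be related to the study drug, the monitoring of the AE should be continued"), but the same section also has any AE followed until it resolves or is judged permanent. Section 7.3.5 adds serious events and events leading to discontinuation.
- **Late SAEs.** After the 30-day period, Section 8.2.1.3 asks for a report when the investigator suspects a causal link. That is not the *Related* test of 8.1.3.
- **Dosing.** Maintaining dosing through an unrelated Grade 3 or higher event requires consultation with the Medical Monitor (Section 5.7). Section 6.2 also lets the investigator remove a patient for unmanageable toxicity or another medical reason. The stop for Grade 3 or higher nausea or vomiting does not use relatedness, nor do the platelet, neutrophil and sodium criteria for dosing after discharge.
- **SUSARs.** The sponsor can judge relatedness independently of the investigator.

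All of this is correct and limits the reach of the problem. It does not close the gap: none of these provisions tells the investigator how to label an event in row (c), and the related-AE tables take the investigator's label as it stands.

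A reader might go further and infer that any event COVID-19 could explain is classed as unrelated. The text does not support that. The test is comparative, so a possible alternative cause does not block *Related* when the drug is the more likely one. Nor does 8.1.3 direct row (c) events to *Not related*; it leaves them undefined.

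**Conclusion.** The point holds as a definitional conflict that should be fixed. It is not a threat to the primary endpoint or to the between-arm safety comparison. An event that is a suspected adverse reaction under Section 8.1.1 can have no valid category under Section 8.1.3. What is exposed is the investigator-determined related-AE tables, related TEAEs after 30 days, the investigator's share of SUSAR identification, and the treatment rules that turn on relatedness.

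Two stronger conclusions are tempting and should not be drawn.

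- That drug reactions would go undetected. SAE reporting, DSMB review, the halting criteria and the all-causality tables work without the label.
- That an event must be some multiple more frequent on selinexor than on placebo before it could be called related. That turns an excess fraction across a population into a test of an individual case, whereas an investigator also weighs timing, laboratory course and response to interruption. It reads the comparison as a probability above 50%, although a leading cause among several can sit below that. It also needs background risks that the documents do not give, and one allocation ratio, while SAP Section 7.1.1 says that about the first 50 ITT patients were randomized 2:1 and the rest 1:1.

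The conclusion assumes that the case report form follows 8.1.3 with two categories, as SAP Section 8.1 indicates. How many events fall in the gap is unknown.

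**What to change.** Reconcile Section 8.1.3 with Section 8.1.1 so that the two categories are complementary and rest on the protocol's own standard:

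- *Related*: a reasonable possibility that study treatment caused the event, meaning evidence that suggests causation, even where other causes are also possible.
- *Not related*: no reasonable possibility.

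Cross-refer Section 8.2.1.4 to this definition. Because the change moves some events into *Related*, the sponsor should confirm that the rules in Sections 3.1, 5.7 and 6.2 that refer to relatedness still read as intended. This review proposes no change to those rules.

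The cost is a few sentences in the protocol and site retraining. More AEs will be classed as related in both arms, there will be more SUSAR assessments, and there may be more relatedness-triggered stops of treatment. That last effect should be weighed openly when the wording is changed.

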## **8.2. Serious Adverse Events**

See Section 8.1 for the definition of an SAE. Please note that SAEs that occur at any time between the signing of the Informed Consent Form up to the first dose of study treatment must be reported (in addition to SAEs that occur after the first dose of study treatment).

### **8.2.1.1. Events that Do Not Meet the Definition of a Serious Adverse Event**

Patients are hospitalized as part of the study. If patients are kept in hospital due to a social reason or an administrative reason after they are considered to be discharged, these events will not be considered an SAE. Any other elective hospitalizations to simplify trial treatment or trial procedures or other medical procedures are not considered SAEs

Any sudden explained or unexplained death should be reported as an SAE. Death due to COVID-19 should be reported to the Karyopharm PV department using a SAE form.

### **8.2.1.2. Recording of Serious Adverse Events**

It is the responsibility of the Investigator to record and document all SAEs occurring from the time when the ICF is signed until at least 30 days after the patient has stopped study treatment. All SAEs must be reported on the designated Sponsor's SAE Report Form in addition to being recorded in the eCRF. The original SAE report form must be retained in the Investigator's site file.

All applicable sections of the SAE Report Form must be completed in order to provide a clinically thorough report. The Investigator must assess and record the relationship of each SAE to study treatment and complete the form in English.

See ICH E2A (Clinical Safety Data Management: Definitions and Standards for Expedited Reporting, Attachment 1) for key data elements that are required for expedited reporting.

### **8.2.1.3. Reporting of Serious Adverse Events**

Every SAE, regardless of the causal relationship to the study treatment, occurring after the patient has signed informed consent, until at least 30 days after the patient has stopped study treatment, must be reported to the Karyopharm Pharmacovigilance Department with the timeframe not to exceed 24 hours of the Investigator becoming aware of the event. The investigational site personnel must use the SAE Report Form provided by Karyopharm for reporting any SAE to the Karyopharm Pharmacovigilance Department.

Upon completion, the SAE Report Form must be immediately emailed or faxed to:

Pharmacovigilance Department  
Karyopharm Therapeutics Inc.  
Email: [[contact]](mailto:[contact])  
[contact] (USA)  
[contact] (Germany)

Any SAE observed after the 30-day follow-up period should only be reported to Karyopharm if the Investigator suspects that the SAE has a causal relationship to the study treatment. Recurrent episodes, complications, or progression of the initial SAE must be reported, as follow-up to the original episode, within 24 hours of the Investigator receiving the follow-up information.

An SAE should be followed until its resolution or until it is judged to be permanent. An assessment should be made at each study visit (or more frequently, if necessary) of any changes in severity of the event, the suspected relationship to the study treatment, the interventions required to treat the event, and the outcome of the event.

#### **8.2.1.4. Suspected Unexpected Serious Adverse Reactions**

Suspected unexpected serious adverse reactions (SUSARs) are SAEs that are unexpected and judged by the Investigator or Karyopharm to be related to the study treatment administered. All SUSARs will be collected and reported to the competent authorities and relevant ethics committees in accordance with the FDA's "Safety Reporting Requirements for Investigational New Drugs and Bioanalytical/Bioequivalence Studies" or as per national regulatory requirements in participating countries.

If required by local regulations, the Investigator is responsible for notifying his/her IRB or local ethics committee of all SAEs.

### **8.3. Procedures for Handling Special Situations**

#### **8.3.1. Pregnancy and Breastfeeding**

Note: Pregnancy per se is not considered to be an AE; however, it is discussed here because of the importance of reporting pregnancies that occur during studies and because a medical occurrence observed in the mother or fetus/newborn would be classified as an AE.

Female patients of childbearing potential and fertile male patients will be informed as to the potential risk of conception while participating in this study and will be advised that they must use highly effective contraception listed below (i.e., results in a low failure rate when used consistently and correctly) during the dosing period and for a period of at least 3 months after the end of treatment.

Highly effective methods include:

- Combined (estrogen and progestogen containing) hormonal contraception associated with inhibition of ovulation:
  - Oral
  - Intravaginal
  - Transdermal
- Progestogen-only hormonal contraception associated with inhibition of ovulation:
  - Oral
  - Injectable
  - Implantable
- Intrauterine device
- Intrauterine hormone-releasing system
- Bilateral tubal occlusion

- Vasectomized partner
- Sexual abstinence

If a patient is confirmed pregnant during the study, study drug administration must be discontinued immediately. The Investigator must immediately notify the Sponsor's Medical Monitor of the event and record the pregnancy on the Pregnancy Form (provided by Karyopharm). The initial information regarding a pregnancy must be forwarded to Karyopharm's Pharmacovigilance by email or fax within 24 hours of first knowledge of its occurrence.

The pregnancy should be followed up to determine the outcome, including any spontaneous or voluntary termination, details of the birth, and any birth defects, congenital abnormalities, or maternal and/or newborn complications.

All pregnancies occurring within 3 months after the patient's last dose of study drug must be reported to Karyopharm, regardless of whether the patient received selinexor or other study drugs, withdraws from the study, or the study is completed. Patients should be instructed to inform the Investigator regarding any pregnancies.

Any SAE that occurs during pregnancy must be recorded on the SAE report form (e.g. maternal serious complications, therapeutic abortion, ectopic pregnancy, stillbirth, neonatal death, congenital anomaly, or birth defect) and reported within 24 hours in accordance with the procedure for reporting SAEs (described in Section 8.2.1.3 ).

A pregnancy in a female partner of a male patient must be reported to Karyopharm within 24 hours of learning of its occurrence. Pregnancies in female partners should only be followed if the male patient is being treated with a selinexor-containing regimen. Consent to report information regarding these pregnancy outcomes should be obtained from the female partner.

It is not known whether selinexor passes into the breast milk. Mothers should not breastfeed while being treated with selinexor-containing regimen.

### **8.3.2. Abuse, Misuse, Medication Errors and Overdose**

All incidences of abuse, misuse, medication errors and overdose are to be reported to Karyopharm Pharmacovigilance on an SAE report form to [contact], regardless of whether or not there is an associated AE or SAE.

#### **8.3.2.1. Overdose**

An overdose is a deliberate or accidental administration of any study treatment to a study patient, at a dose greater than that which was assigned to that patient per the study protocol. If an overdose occurs, the Investigator and Karyopharm should be notified immediately, and the patient should be observed closely for AEs. Resulting symptoms should be treated, as appropriate, and the incident of overdose and related AEs and/or treatment should be documented in the patient's medical record and in the eCRF. Information regarding the overdose is to be recorded on an SAE report form and sent to Karyopharm Pharmacovigilance, regardless of whether or not an AE or SAE has occurred due to the overdose. If the overdose is associated with an SAE, the SAE report form must be submitted to Karyopharm Pharmacovigilance within 24 hours of awareness. If there is no AE or SAE, the report must be submitted as soon as possible.

Doses of selinexor of up to 160 mg per week (80 mg twice weekly, the approved dose in RRMM) and weekly doses of up to 100 mg have been given to patients with advanced cancers with adequate tolerability. No specific antidotes for overdose are known at this time.

